10.5 Interim Analysis and Data Monitoring

An interim analysis will be performed to review safety data after at least 100 pediatric subjects (<18 years of age) have reached 48 weeks of potential active study drug treatment, inclusive of active study drug treatment in one of three parent (i.e., pivotal and maximal use) studies. All summaries will be produced for interim analysis.

The final analysis will be conducted after study completion (i.e., the last subject's last visit) and database lock.

10.6 Examination of Subgroups

For the following efficacy outcomes:

1. Proportions of subjects who achieve vIGA-ADTM=0 at least 1 time during the study (for subjects entering the study with a vIGA-ADTM score ≥ 1):
2. [REDACTED]
3. vIGA-ADTM scores at Week 48 (LOCF)

4. [REDACTED] change and percent change from Baseline in %BSA affected at Week 48 (LOCF)
5. [REDACTED] change and percent change from Baseline in EASI score at Week 48 (LOCF)

Subgroup analyses will be generated for the following groupings:

- Baseline vIGA-AD™
- Age (2-6 yrs, 7-11 yrs, 12-17 yrs, ≥ 18 yrs)
- Sex
- Race (White, Asian, Black or African American, and Other)
- Baseline %BSA affected (<10%, 10%-<20%, 20%-<30%, $\geq 30\%$)
- Duration of disease (<2 yrs, 2-5 yrs, >5 yrs)
- Prior Systemic AD Medication
- Country (USA and Canada)

Race subgroup “Other” includes “American Indian or Alaska Native”, “Native Hawaiian or other Pacific Islander” and “Multiple Races Checked”,

10.7 Multiple Comparison/Multiplicity

No adjustments for multiplicity will be made in this study.

10.8 Multicenter Studies

This is multicenter study, with up to approximately 135 sites in the US and Canada participating in the study. Up to 961 subjects will be enrolled in this study across all regions, including up to 836 rollover subjects from studies DMVT-505-3101, DMVT-505-3102, and DMVT-505-2104 and approximately 125 subjects directly enrolling into this study.

Efficacy endpoints will be summarized by country.

12. PHARMACOKINETIC ANALYSES

No pharmacokinetic analysis is planned for this study.

13. SAFETY ANALYSES

All safety analyses will be based on the ITT population. Definition of baseline values is outlined in section 10.2.

13.1 Extent of Exposure

Subjects will be characterized by a series of treatment periods as defined in Section 10.1. These treatment period definitions are based on attainment of specified vIGA-AD™ values.

The following exposure and compliance parameters will be summarized descriptively:

- Total expected number of days exposed, calculated as the sum of number of days over all treatment periods.
- Total number of doses administered within treatment periods, calculated from the subject dose diary including in-clinic dosing and summed over all treatment periods. If a subject returns no diary records, then the number of home doses is assumed to be 0. If a subject has no clinic visits where study drug was administered, then the number of clinical doses is assumed to be 0.
- Percent compliance will be calculated as the (total number of doses administered within treatment periods) / (total expected number of days exposed) * 100.
- Subject compliance, defined as $\geq 80\%$ compliance while enrolled in the study. If the percentage of study medication compliance cannot be computed, the subject is assumed to be less than 80% compliant.

In addition, the following exposure parameters will be summarized descriptively for the entire study (regardless of vIGA-AD™ status):

- Total number of doses administered, calculated from the subject dose diary and in-clinic dosing. If a subject returns no diary records, then the number of home doses is assumed to be 0. If a subject has no clinic visits where study drug was administered, then the number of clinical doses is assumed to be 0.
- Grams (g) of study drug administered. Drug administered is calculated as the summation of the difference between dispensed weight and returned weight for all returned tubes. Unreturned/unopened tubes will be assumed unused and will be included as 0 grams in the amount drug used calculation. Average grams of study drug administered per dose will be calculated as the total grams / total number of doses administered. Subjects that had no diaries returned will not have average grams per dose reported.

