5.1.5.3 Application of Study Drug

Study drug will be dispensed to subjects or their caregivers at the clinical site in appropriately labeled tubes.

Subjects or caregivers will take the tubes home and self-administer study drug (or have caregiver apply if necessary) to affected areas QD, except on clinic visit days when study drug is applied under supervision at the site.

Subjects will be instructed to apply study drug as follows:

- QD application to affected areas; subjects or their caregivers are advised to choose the application time they prefer and to apply the study drug at that approximate time each day of study participation. Subjects should avoid dosing around midnight to avoid potentially dosing twice in one calendar day.
- If a subject misses a daily dose, it will be recorded as a protocol deviation. The subject should continue dosing the next day and should not apply more than once daily to make up for the missed dose on the previous day. If a dose is missed, the missed dose and the reason for the missed dose should be recorded in the daily diary as such. Itch rating can still be recorded in the diary even if a daily dose was missed.
- Study drug should be applied to dry, clean skin.
- Study drug may be applied to skin around the eye but avoid direct contact with the eye – study drug is not for ophthalmic use.
- Wash hands after application, unless treating lesions on the hands.

- Study drug should be applied to all lesions, including newly appearing lesions and lesions/areas that improve during the study until a vIGA-AD™ of 0 is achieved. Once a vIGA-AD™ of 0 is achieved, the treatment period ends. If/when disease worsening occurs, and treatment is re-initiated at a vIGA-AD™ of ≥ 2 , all lesions currently present and any new lesions that occur during the new treatment period should be treated. A body diagram identifying locations of lesions may be provided to the subject and/or caregiver.
- Subjects are allowed, but not required, to treat scalp lesions with study drug; however, efficacy analyses will not include assessment of AD in this area.
- If there is residual cream visible on the disease-affected lesional skin, then the subject or caregiver should be instructed to continue to lightly rub the cream into the skin until it is no longer visible.
- If study drug is applied to the subject by another person, that person should thoroughly wash his/her hands after application.

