7.2 Visit 1; Baseline (Day 1)

7.2.1 Baseline Visit for Subjects Rolling Over from DMVT-505-3101 and DMVT-505-3102

On Day 1, subjects from the parent studies DMVT-505-3101 or DMVT-505-3102 who were considered eligible for this study will sign the ICF and be reassessed to confirm eligibility to participate in this study. All subjects who continue to meet study eligibility criteria will be enrolled. Subjects entering with a vIGA-AD™ ≥ 1 will receive treatment with tapinarof cream, 1% until they achieve a vIGA-AD™ score of 0, at which time treatment will be discontinued and subjects monitored for maintenance of the remittive effect. If/when

disease worsening occurs, as evidenced by a vIGA-AD™ ≥ 2 , treatment will then be re-initiated and continued until a vIGA-AD™ of 0 is observed. Subjects entering with a vIGA-AD™ of 0 will have treatment discontinued beginning at the Baseline visit and will be monitored for maintenance of the remittive effect.

The following procedures and assessments will be performed at the Baseline visit:

- Demographics and Fitzpatrick skin type (carried over from parent study)
- Medical history (carried over from parent study)
- Brief physical exam (last assessment from parent study)
- Vital signs measurements (last assessment from parent study)
- Urine pregnancy test (WOCBP; last assessment from parent study)
- Blood sample collection for clinical laboratory tests (serum chemistry and hematology; last assessment from parent study)
- Urinalysis (last assessment from parent study)
- vIGA-AD™ score (excluding subject's scalp; last assessment from parent study)
- %BSA affected calculation (excluding subject's scalp; last assessment from parent study)
- EASI (excluding subject's scalp; last assessment from parent study)
- [REDACTED]
- [REDACTED]
- [REDACTED]
- PP-NRS (last assessment from parent study)
- [REDACTED]
- [REDACTED]
- [REDACTED]
- Photography of a representative area of the subject's disease area (at a subset of study sites only; last photograph from parent study)
- AE recording (ongoing from parent study at the time the ICF is signed in this study)
- Concomitant medication recording (ongoing from parent study at the time the ICF is signed in this study)
- Dispense diary (subjects or their caregivers will be instructed in how and when to complete diary)
- Dispense study drug, if applicable
- Instruction on how to apply study drug, if applicable
- Study drug application under supervision, if applicable

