Rollover subjects in this study will begin treatment based on their validated Investigator Global Assessment for Atopic Dermatitis (vIGA-ADTM) score from the final visit in one of the three aforementioned studies (DMVT-505-3101, DMVT-505-3102, or DMVT-505-2104). Subjects entering with a vIGA-ADTM ≥ 1 will receive treatment with tapinarof cream, 1% once daily (QD) until they achieve a vIGA-ADTM score of 0, at which time treatment will be discontinued and subjects monitored for maintenance of disease control (i.e., the extent of the remittive effect). If/when disease worsening occurs, as evidenced by a flare to vIGA-ADTM ≥ 2 , treatment will then be re-initiated and continued until a vIGA-ADTM of 0 is achieved. Subjects entering with a vIGA-ADTM of 0 will have treatment discontinued beginning at the Baseline visit and will be monitored for maintenance of the remittive effect. If/when disease worsening occurs, as evidenced by a vIGA-ADTM ≥ 2 , treatment will then be re-initiated and continued until a vIGA-ADTM of 0 is achieved. This treatment and re-treatment pattern of use will be continued until the end of the study (i.e., subjects may receive study treatment up until the Week 48 visit).

Subjects enrolling directly into this study will receive treatment QD with tapinarof cream, 1% beginning at Baseline and continue treatment until they achieve a vIGA-ADTM score of 0, at which time treatment will be discontinued and subjects monitored for maintenance of the remittive effect. If/when disease worsening occurs, as evidenced by a flare to vIGA-ADTM ≥ 2 , treatment will be re-initiated and continued until a vIGA-ADTM of 0 is achieved. This regimen of treatment and re-treatment will continue until the end of the study (i.e., subjects may receive study drug up until the Week 48 visit).

Study drug will be dispensed to subjects or their caregivers, applied during the clinic visits, and applied at home between clinic visits as instructed by site personnel. Subjects or their caregivers will be instructed to apply study drug QD to all affected areas, including newly appearing lesions and lesions/areas that improve during the study until a vIGA-ADTM of 0 is achieved. Once a vIGA-ADTM of 0 is achieved, the treatment period ends. If/when disease worsening occurs, and treatment is re-initiated at a vIGA-ADTM of ≥ 2 , all lesions currently present and any new lesions that occur during the new treatment period should be treated.

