8. ANALYSIS SETS

The following subject population will be used for safety and efficacy analyses:

- The intent-to-treat (ITT) population will include all subjects enrolled into the study.

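### The SAP 13.1 compliance default counts a rollover subject who enters clear and never needs treatment as less than 80% compliant

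*SAP*

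**What the plan says.** SAP 13.1 defines percent compliance as the ratio "total number of doses administered within treatment periods) / (total expected number of days exposed", times 100. Expected days are the days summed over a subject's treatment periods, and of those periods the section says: "These treatment period definitions are based on attainment of specified" vIGA-AD values, with the definitions themselves placed in SAP 10.1. A subject is compliant at 80% or more. For the remaining case: "If the percentage of study medication compliance cannot be computed, the subject is assumed to be less than 80% compliant".

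Under SAP 4, rollover subjects who enter at vIGA-AD 0 "will have treatment discontinued beginning at the Baseline visit and will be monitored for maintenance of the remittive effect"; treatment restarts only if the score reaches 2 or more. Protocol 7.2.1 accordingly makes the Baseline supply conditional for rollovers: "Dispense study drug, if applicable".

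The table population comes from two statements. SAP 13: "All safety analyses will be based on the ITT population". SAP 8: "The intent-to-treat (ITT) population will include all subjects enrolled into the study". Having been dosed is not a condition.

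**The concern.** The default does two jobs. For a subject who was on treatment but whose percentage cannot be worked out, it is an ordinary conservative rule, and it is not disputed here. For a subject who was never due any treatment, it turns an undefined ratio into a finding of non-compliance. That subject missed nothing. Protocol 5.1.5.3 says "If a subject misses a daily dose, it will be recorded as a protocol deviation", and here there is no such dose to record.

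The design anticipates this group. Protocol 10.4.2 lists, for subjects entering clear, the proportion who never worsen to vIGA-AD 2 or more, and SAP 9.1 counts subjects who apply any study medication separately from those enrolled.

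Three things follow for the reader of the compliance table:

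- The proportion at 80% or more mixes missed doses with absence of relapse, which is a favourable outcome.
- The continuous summary of percent compliance has no value for these subjects, while the categorical line counts them below 80%. The two adjacent lines then describe different sets of subjects.
- Columns with different never-treated shares would differ in reported compliance with no difference in how the drug was used. The columns in question are prior tapinarof, prior vehicle and DMVT-505-2104. Because SAP 10.5 produces all summaries at the interim, the same line would appear there too.

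**Working it through.** The documents state no compliance figure, so there is nothing to reproduce. The check applies the SAP 13.1 rule to test subjects and then works out the effect on a column.

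**Step 1: the rule applied to single subjects.** Percent = doses within treatment periods / expected days × 100.

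| Subject | Doses / expected days | Percent | Class |
|---|---|---|---|
| Treated, fully adherent (illustration) | 56 / 56 | 100% | at least 80% |
| Enters at 0, never restarts, no treatment period | 0 / 0 | undefined | below 80%, by the default |
| Same subject, if SAP 10.1 assigned a nominal one-day period | 0 / 1 | 0% | below 80%, by calculation |

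The third row tests how far the result depends on the SAP 10.1 text that cannot be seen. Zero days leads to the default, and any positive number of days d gives 0/d = 0%. Only an explicit exception changes the class.

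**Step 2: who is affected.** The route is open to rollover subjects who enter at 0 and either stay below vIGA-AD 2 or leave the study before reaching it. Direct enrollers all start treatment at Baseline (Protocol 5.1.5.1), so it does not reach them.

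**Step 3: effect on a column.** Let a column hold N subjects, of whom m have zero expected days and k are truly at 80% or more.

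- Proportion among subjects with expected days: true = k / (N − m)
- Proportion as reported: k / N = true × (1 − s), with s = m / N

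For Total (Overall), direct enrollers dilute the effect. SAP 5 gives up to 836 rollovers and about 125 direct enrollers, and 836 + 125 = 961. The overall never-treated share is therefore s × 836/961 = s × 0.870.

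Neither s nor the true proportion is in the documents. With an assumed true proportion of 90%:

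| s among rollovers | Rollover column | Overall share | Total (Overall) |
|---|---|---|---|
| 1% | 0.90 × 0.99 = 89.1% | 0.87% | 0.90 × 0.9913 = 89.2% |
| 5% | 0.90 × 0.95 = 85.5% | 4.35% | 0.90 × 0.9565 = 86.1% |
| 10% | 0.90 × 0.90 = 81.0% | 8.70% | 0.90 × 0.9130 = 82.2% |

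Across assumed true proportions from 70% to 95%, with s = 5%:

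- Rollover column: loss of 0.70 × 5 = 3.5 to 0.95 × 5 = 4.75 points
- Total (Overall): loss of 0.70 × 4.35 = 3.0 to 0.95 × 4.35 = 4.1 points

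**Step 4: effect between columns.** Take two columns both truly at 90%, one with s = 2% and one with s = 10%. They would read 0.90 × 0.98 = 88.2% and 0.90 × 0.90 = 81.0%, a gap of 7.2 points unrelated to drug use. The two values of s are chosen only to show the mechanism.

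**The case against.** The strongest objection is that the deciding text is out of sight. SAP 13.1 defers to SAP 10.1 for treatment periods, those definitions are not visible in the public version, and they may provide for a subject with no period. On that view this is a point to confirm, not a defect. The limit is real and is why confidence is medium. It does not remove the point: the formula and the default stand in full in 13.1, and the hidden text helps only if it contains an explicit exemption to which 13.1 does not refer.

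The second objection is reach. The study has no hypothesis tests and a single analysis set, and nothing visible uses the 80% class to exclude subjects or to make a decision. The other exposure summaries are not distorted by the default. This stands, and it limits the point to one descriptive line.

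Third, disposition already reports how many subjects apply any study medication, so a reader could approximate the treated-only figure. That is a partial remedy: a subject who had treatment days but applied nothing also falls outside that count, and properly belongs below 80%.

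Fourth, the sizes are hypothetical. They are, and they are offered only as illustrations.

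Two narrower criticisms are fair. The missed-dose rule in Protocol 5.1.5.3 does not define compliance for the SAP, so it shows a poor fit and not a contradiction. And the affected group includes subjects who leave before worsening, so not all of them have shown disease control through the study.

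**Conclusion.** The point holds on the visible text. As written, SAP 13.1 classes a rollover subject who enters clear and never restarts as less than 80% compliant, although no dose was ever due. This is a stated rule giving a wrong classification, not a missing detail. It rests on one assumption: that SAP 10.1 contains no explicit exception for subjects without a treatment period.

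The consequence is limited to the proportion at 80% or more in the rollover and total columns, which is understated by the factor (1 − s). Its size cannot be fixed from the documents, since they do not give the never-treated share. No test, analysis set or adverse-event denominator shown depends on it. No breach of SAP 6 is claimed, because that section allows denominators to vary. The change should be made because the error is clear and the remedy nearly free.

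**What to change.** In SAP 13.1, state that when total expected days exposed is zero, compliance is reported as not applicable, the subject is left out of the denominator for the 80% class, and the number of such subjects is shown in each column. Keep the below-80% default for subjects who had treatment periods but whose percentage cannot be computed. Section 13.1 already works this way elsewhere: average grams per dose is not reported for subjects who returned no diaries.

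If SAP 10.1 already exempts these subjects, a cross-reference in 13.1 is enough. If it instead gives them nominal days, word the exception to cover subjects for whom no treatment was due.

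The cost is one sentence in the SAP and one count row in the compliance table. No new data are needed and no clinical rule changes.

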5.4 Compliance with Study Drug Administration

At Baseline, study staff will provide the subject or caregiver with detailed instructions concerning protocol requirements and use of study drug. Additionally, subjects or caregivers will be asked to complete a daily diary with the time of each application of study drug, except on study visit days. At each post-Baseline study visit, study staff will review use of study drug, as applicable, with the subject or caregiver. Subject compliance will be assessed via study diary completion.

When subjects are dosed at the site, they and/or their caregiver will apply the study drug under supervision of the study staff. The date and time of each dose administered in the clinic will be recorded in the source documents. The study drug and study subject identification should be confirmed at the time of dosing by a member of the study site staff other than the person dispensing the study drug.

At the time of dispensing study drug to each subject, site personnel will weigh the tubes to be dispensed with the cap on and will record the weight of all tubes dispensed at each visit in the drug accountability logs.

Subjects and/or caregivers will be instructed to bring all used and unused tubes with them to each study visit. Site personnel will weigh the returned tubes (used and unused) with the cap on and record the weight in the drug accountability logs. If a tube has been lost, discarded, or forgotten by the subject, then the site personnel will make a notation of this on the drug accountability logs. Forgotten tubes should be returned by the subject at the next study visit. Tubes of study medication dispensed at the most recent prior visit which remain unopened (the foil cap on the tube remains fully intact/undisturbed) may be re-dispensed to study subjects at the current visit. Unopened tubes may only be re-dispensed once. Opened, partially used tubes or tubes with foil overlay removed are not to be re-dispensed to study subjects. If there is any question as to re-dispensation, sites should issue new tubes of study medication to the subject(s).

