6.5 Virtual Assessments

In the event that a subject cannot attend their regularly scheduled study visits in person due to a COVID-19-like situation necessitating a limit on in-person contact, the Investigator may perform safety and efficacy assessments by phone or video. Source documentation should note if the visit was performed by phone or by video. The Investigator may use the technology platform that is currently available to them. Suggested platforms include Apple FaceTime, Zoom for Healthcare, Facebook Messenger video chat, Microsoft Teams, Google Hangouts video, and Skype. Additional details of the visit should be included in source documentation, as detailed in the Study Reference Manual.

If the subject can only be contacted by phone, the following should be assessed or performed:

- AEs
- Concomitant Medications
- Reminder to complete diary
- Instruction not to discard empty tubes of study drug

If the subject has video capabilities, the following items should be assessed or performed:

- AEs
- Concomitant Medications
- vIGA-AD™ assessment (excluding subject's scalp)
- %BSA assessment (excluding subject's scalp)
- EASI (excluding subject's scalp)
- [REDACTED]
- [REDACTED]
- Application of study drug by the subject or caregiver, if applicable
- Completion of the PP-NRS (the subject or caregiver [as applicable] can verbally indicate the answer which the study coordinator will document in the source document).
- Reminder to complete diary
- Instruction not to discard empty tubes of study drug

The reason that assessments cannot be completed during a virtual assessment (i.e., labs, vital signs, physical exams, etc.) must be noted (e.g., COVID-19) and the missed assessments will be recorded as protocol deviations.

7 Timing of Procedures and Assessments

This section lists the procedures and assessment to be performed at scheduled time points during the study as outlined in the Schedule of Assessments (Table 1). Information on study procedures and assessments is provided in Section 6.

- Any change in timing or any addition of a time point(s) for any planned study assessment must be documented in a “Note to File,” which is approved by the relevant Sponsor study team member and then archived in the study Sponsor and site study files; this will NOT constitute a protocol amendment.
- The IRB/IEC will be informed of any safety issues that require alteration of the safety monitoring or amendment of the ICF.

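### SAP 13.1 counts a tube that is never returned as 0 g used but keeps its recorded doses in the grams-per-dose denominator, so total grams is a lower bound reported as the amount administered.

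*SAP*

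**What the plan says.** SAP 13.1 defines the quantity of drug over the entire study, whatever the vIGA-AD status. The numerator is: "Drug administered is calculated as the summation of the difference between dispensed weight and returned weight for all returned tubes". The next sentence deals with the other tubes: "Unreturned/unopened tubes will be assumed unused and will be included as 0 grams in the amount drug used calculation". The ratio follows: "Average grams of study drug administered per dose will be calculated as the total grams / total number of doses administered". Its denominator is: "Total number of doses administered, calculated from the subject dose diary and in-clinic dosing". Nothing links that dose count to whether the tubes came back.

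The only exclusion from the ratio concerns diaries: "Subjects that had no diaries returned will not have average grams per dose reported". There is no matching exclusion for missing tubes.

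Protocol 5.4 has subjects bring used and unused tubes to each visit, where they are weighed with the cap on. It foresees tubes that do not come back, which the site records in its accountability log: "If a tube has been lost, discarded, or forgotten by the subject, then the site personnel will make a notation of this on the drug" (sentence cut here). It also asks that forgotten tubes be brought to the next visit. For virtual visits by phone or video, Protocol 6.5 lists: "Instruction not to discard empty tubes of study drug". The SAP makes no use of the log notations.

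**The concern.** One zero is applied to two different situations. For a tube returned unopened, 0 g is a fact, and the weight difference would give it anyway. For a tube that is never returned, 0 g is an assumption. The protocol gives no support for it, since it names discarded tubes as one way in which tubes go missing and warns against throwing away empty ones. In practice the sentence therefore matters only for unreturned tubes.

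The ratio has a further fault. Drug from a missing tube leaves the numerator, while the doses applied from it remain in the denominator, so the two cover different amounts of treatment. The SAP accepts this logic for diaries, because it withholds the ratio when none is returned, but it does not apply it to tubes.

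What is at stake is a descriptive exposure figure. In the readable text, tube weight is the only planned measure of how much cream was applied, and SAP 12 plans no pharmacokinetic analysis. A reader of the study report would take the figure as the amount used.

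**Working it through.** The plan states no figure to reproduce, so the check follows the rule through algebraically and then with assumed numbers.

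**Inputs from the documents**
- Tube content: 30 g (Protocol synopsis, Investigational Product).
- Grams: dispensed minus returned weight, returned tubes only; never returned = 0 g (SAP 13.1).
- Doses: all diary plus in-clinic doses (SAP 13.1).
- Treatment: once daily for up to 48 weeks, with visits every 4 weeks, i.e. 12 intervals of 28 days.

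**Inputs assumed, because the documents do not give them**
- Share of tubes never returned.
- Use per dose: 4 tubes fully used per 28 doses, with continuous treatment.

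**Formulas.** Let u be the share of drug actually used that came from never-returned tubes, and m the share of applied doses missing from the diary.
- Reported grams / true grams = 1 - u.
- Reported grams per dose / true grams per dose = (1 - u)/(1 - m). With complete diaries (m = 0) this is also 1 - u.

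**Whole study.** True use is 12 x 4 = 48 tubes, or 48 x 30 = 1440 g, over 12 x 28 = 336 doses: 1440/336 = 4.29 g per dose.

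| Used tubes never returned | Reported grams | Reported g/dose | Error in both |
|---|---|---|---|
| 0 | 1440 | 4.29 | 0 |
| 1 | 1410 | 4.20 | -2.1% |
| 2 | 1380 | 4.11 | -4.2% |
| 3 | 1350 | 4.02 | -6.25% |
| 48 (all) | 0 | 0.00 | -100% |

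The last row is a subject who returns every diary and no tube.

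**Fewer tubes.** Treatment stops at vIGA-AD 0, so many subjects may use far fewer than 48 tubes. One fully used tube lost is -8.3% of 12 used, -12.5% of 8, -25% of 4 and -50% of 2.

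**Incomplete diaries.** At u = 5%, the error in grams per dose is:
- m = 0: -5.0%
- m = 2%: 0.95/0.98 - 1 = -3.1%
- m = 5%: 0%
- m = 10%: 0.95/0.90 - 1 = +5.6%

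**Effect of the remedy.** Suppose the three lost tubes fall in three different intervals. The nine complete intervals give (9 x 120)/(9 x 28) = 1080/252 = 4.29 g per dose, the true value here. The range for total grams runs from 1350 g (unreturned = 0 g) to 1350 + 3 x 30 = 1440 g (unreturned = full content).

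**Wording.** The slash in the SAP sentence might be read as covering only tubes that are both unreturned and unopened. That does not help: the sum already runs over returned tubes only, so any tube never returned adds nothing.

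**The case against.** The case for leaving the rule alone is that little depends on it and that the loss may be small.

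- **Recovery of tubes.** Tubes forgotten at one visit are due at the next and are then weighed. The instruction about empty tubes is a safeguard against loss and does not show that loss occurs. This stands: the point concerns only tubes that never come back, and how many were used is not known.
- **Consequences.** The study is descriptive. Days exposed, dose counts and percent compliance do not use grams. The interim trigger counts subjects and weeks of treatment, and no readable endpoint or adverse event summary is broken down by grams. A reader might infer that the rule undermines the ICH E1A basis of the sample size. The documents do not support that: the trigger and duration-based exposure are untouched, and the rule cannot inflate total grams.
- **Size.** A reader might take an error of 25% or 50% from one tube in a single four-week interval. SAP 13.1 reports over the entire study, so such figures apply only to a subject who used four or two tubes in all.
- **Who is affected.** A reader might expect the worst distortion in extensive disease. By the formula, each lost tube costs a heavy user a smaller percentage. A larger relative error would need heavy users to lose a larger share of their tubes, and nothing in the documents shows that.
- **Direction.** Grams per dose cannot be called biased low without qualification, since unrecorded doses raise it. This too stands, but two gaps that happen to offset each other do not make the ratio sound.

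None of this makes 0 g a measurement of what was used from a missing tube.

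**Conclusion.** The point holds in a limited form. Under SAP 13.1 total grams is a lower bound reported as the amount administered: exact if every never-returned tube was unused, too low otherwise, and never too high because of this rule. With complete diaries, grams per dose is understated by the same share u. With incomplete diaries its net direction is not fixed.

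The size cannot be derived from the documents. The figures of -2.1%, -4.2% and -6.25% for one, two or three lost tubes rest on an assumed 48 fully used 30 g tubes and complete diaries. The percentages grow as the number of tubes used falls, up to a reported 0 g and 0 g per dose for a subject who returns diaries but no tubes. This is a defect in a descriptive exposure summary, worth correcting because the correction is cheap. It does not call the duration of exposure, compliance or the adverse event summaries into question.

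**What to change.** In SAP 13.1:

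1. Keep 0 g only for tubes returned unopened. Treat use from a never-returned tube as missing.
2. Report the number of unreturned tubes, and total grams as a range from unreturned = 0 g to unreturned = full dispensed content. The labelled 30 g can serve as full content, since Protocol 5.4 records weights with the cap on.
3. Report grams per dose for subjects with all dispensed tubes returned. Alternatively, compute it over intervals with all tubes returned, using the doses of those same intervals, where re-dispensed and late-returned tubes can be assigned to an interval.
4. Give grams per dose for all subjects under both ends of the range in item 2 as a sensitivity summary.

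The cost is SAP wording and some programming on the dispensed and returned weights that the existing calculation already needs. The log notations on why a tube is missing are not required, which helps because the documents do not show whether they reach the database. The disadvantages are fewer subjects or intervals in the grams-per-dose average, possible selection from restricting to them, and a range in place of one figure for total grams. The range does not correct for unrecorded diary doses.
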